Study to Evaluate the Safety and Efficacy of Oral Insulin Formulation in Type 2 Diabetes Mellitus Subjects

NCT06473662

06/19/2024

STUDY OBJECTIVES

Primary Objective

To evaluate the safe and effective dose of USVCAP (75 IU, or 150 IU, or 300 IU) after twice daily treatment with selected fixed dose (75 IU, or 150 IU, or 300 IU) of USVCAP for 12 weeks

Secondary Objective

To assess the immunogenicity of the investigational product

INVESTIGATIONAL PLAN

Overall Study Design and Plan-Description

Overview of Study Design

This was a phase IIb, open-label, randomized, comparative study to evaluate the safety and efficacy of USVCAP formulation in T2DM subjects uncontrolled with metformin hydrochloride treatment.

Total of 153 subjects who met the eligibility criteria were randomized in a ratio of 1:1:1 to any one of the following 3 treatment groups:

- Group A: USVCAP 75 IU, BD for 12 weeks
- Group B: USVCAP 150 IU, BD for 12 weeks
- Group C: USVCAP 300 IU, BD for 12 weeks

Each subject had following study periods and visits:

- Screening period (Visit 1): It lasted for up to 21 days after signing the informed consent form (ICF)
- Treatment period (Visit 2 to Visit 7): Eligible subjects were randomly assigned to any one of the above treatment groups at Visit 2 by randomization process through an interactive web response system (IWRS). Each subject from all 3 treatment groups received *assigned fixed dose of USVCAP (i.e. IP) as per allocated treatment groups for 12 weeks.

*Assigned fixed dose in the study is defined as: Fixed dose of USVCAP (i.e. IP) administered to subject twice daily for 12 weeks based on the treatment group (Group A, Group B, or Group C) allocated at randomization visit.

- Upon randomization:
 - Subjects allocated to Group A were prescribed with the assigned fixed dose of USVCAP (75 IU BD) from next day of randomization (Day 1) for 12 weeks
 - Subjects allocated to Group B and Group C, underwent a run-in period of 1 week with each previous lower dose/s, prior to initiation of assigned fixed dose of USVCAP. They additionally visited the study site for a step-wise increase of dose/s at each run-in period/s. These visits were called dose escalation (DE) visits (Visit DE 1 and Visit DE 2) in the trial. The dose increase were done once for Group B and twice for Group C subjects as depicted in Table 2 and Table 3. Upon completion of the run-in period/s, the

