The safety of USVCAP formulation in Type 2 Diabetes Mellitus Subjects Uncontrolled with Metformin Hydrochloride Treatment was determined by incidence and severity of treatment emergent adverse events (TEAEs) that occurred during the study period, including occurrence of hypoglycaemic episodes in each treatment group during the study period; and change in laboratory investigations post 12-week administration of USVCAP. Efficacy of the treatment was assessed by change in glycated haemoglobin (HbA1c) level post 12-week twice daily administration of selected fixed dose of USVCAP (75 IU, or 150 IU or 300 IU) from baseline, comparison of change in HbA1c between the 3 fixed dose levels studied to examine dose response relationship post 12-week administration of USVCAP and change in FPG and 2-hour PPG levels in each treatment group post 12-week administration of USVCAP. The immunogenicity was assessed by evaluating incidence of treatment-emergent antibody response (TEAR).

Selection of Study Population

Inclusion Criteria

- 1. Male or female aged 35 to 60 years (both inclusive)
- 2. Type 2 diabetes mellitus diagnosed < 2 years prior to enrolment
- 3. Glycated haemoglobin level $\ge 7\%$ and $\le 9.5\%$
- 4. On stable oral monotherapy with metformin hydrochloride (1000 mg to 2500 mg/day) and regular diet and exercise regimen at least 12 weeks prior to enrolment
- 5. Body mass index between 18 to 30 kg/m2
- 6. Ability to perform capillary blood glucose measurements

- 7. Willing to provide informed and written consent for the clinical trial
- 8. Able to comply with all requirements of clinical trial protocol

Exclusion Criteria

- 1. Subject with history or evidence of hypersensitivity to insulin or metformin hydrochloride or its excipients
- 2. Suffering from type 1 diabetes mellitus
- 3. Received treatment with sulphonylureas or alphaglucosidase inhibitors, Glucagon-like peptide-1 (GLP-1) receptor agonists or Sodium-glucose co-transporter 2 (SGLT2) inhibitors or meglitinides or pramlintide or thiazolidinediones within 3 months prior to enrolment
- 4. Previously treated with insulin within 3 months prior to enrolment
- 5. History of episodes of hypoglycaemia during 3 months prior to enrolment.
- 6. Reduced awareness of hypoglycaemia or inability to identify and tackle hypoglycaemic episodes
- 7. History of substantial weight loss defined as 5% decrease in body weight within the last 6 months
- 8. Medical history of unstable angina within 1 year prior to enrolment

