- Renal function tests: Serum creatinine, BUN, sodium, potassium, chloride, and eGFR. Serology tests: human immunodeficiency virus, hepatitis B virus, and hepatitis C virus tests (only at Visit 1)
- At Visit 1, 7 and 8
 - Urine samples were collected for: Urine pregnancy test (UPT): Only for females of childbearing potential or who are ≤ 1 year postmenopausal prior to enrolment
- At Visits, 1, 3, 4, and 6:
 - Fasting plasma glucose level (also prior to dosing at Visit DE 1 and DE 2);
 - 2-hour PPG level (also prior to dosing at Visit DE 1 and DE 2)
- At Visit 1 only:
 - Haematology: RBCs count, Hb, platelet count, WBCs count including differential count (only at Visit 1)
 - Serology tests: human immunodeficiency virus (HIV), hepatitis B virus (HBV), and hepatitis C virus (HCV) tests
 - Urinalysis: routine examination (also at Visit 8)
 - Urine samples were collected for the following tests
 - At Visit 1, 7, and 8: Urine pregnancy test (UPT): Only for females of childbearing potential or who are ≤ 1 year postmenopausal prior to enrolment
 - At Visit 1 only: Urinalysis: routine examination

Any additional laboratory tests if required during the study period could be done at local accredited laboratory.

Immunogenicity Assessment: Insulin Antibody test - Anti-insulin antibody (AIA)

The immunogenicity of the IP was assessed using validated assays. Blood samples (1 x 3.5 mL) were collected at screening visit (Visit 1), End of treatment visit (Visit 7) and Post treatment follow-up visit (Visit 8) for testing presence of anti-insulin antibodies to the IP. The procedure for sample handling, storage and analysis was provided in the central laboratory manual.

Emergency Contact

In case of any emergency, the site contacted the medical monitor from the CRO. The medical monitor provided guidance in case of any emergency related to safety of the subject.

Other Study Assessment

Body Weight, Waist circumference and Body mass index

Body weight was measured at every study visit in kg. Body mass index (BMI) (kg/m^2) and waist circumference (cm) was calculated at all study visits, except Visit DE 1 and Visit DE 2.

Body mass index (BMI) was calculated by formula:

$$BMI = \frac{Weight \ (kg)}{height^2 \ (m)^2}$$

Appropriateness of Measurements

All clinical measurements were performed using standard methods that were generally recognized as being reliable, accurate, and relevant.

Primary Variable(s):

Efficacy Assessment:

- Glycated haemoglobin (HbA1c)

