- Fasting plasma glucose (FPG)
- 2-hour post prandial plasma glucose (2-hour PPG)

Safety Assessments:

- AEs and SAEs (serious and non-serious AEs) were collected for relatedness, severity, seriousness, and outcome, including events of hypoglycaemia were collected once the signed informed consent was obtained from the subject
- Vital signs: Pulse rate (PR), respiratory rate (RR), systolic blood pressure (BP) and diastolic BP (in supine position after 5 minutes of rest), and body temperature (at all visits)
- Physical examination 12-Lead electrocardiogram (ECG)
- Laboratory investigations:
 - Lipid profile: Total cholesterol, high density lipoprotein (HDL), low density lipoprotein (LDL) very low-density lipoprotein (VLDL) and triglycerides after at least 12 hours of fasting
 - o Liver function tests: ALT, AST, and total bilirubin
 - Renal function tests: serum creatinine, eGFR, sodium, potassium, chloride, and BUN
 - Urine pregnancy test (UPT): Only for female subjects who are of childbearing potential or who are ≤ 1 year postmenopausal prior to enrolment in the study.

The Investigator described severity, relatedness, and outcome of every AE. The severity of the AE was graded according to NCI-CTCAE version 4.0 on a five- point scale (Grade 1 to Grade 5).

https://evs.nci.nih.gov/ftp1/CTCAE/CTCAE_4.03/Archive/CTCAE_4.0_2009-05-29 QuickReference 8.5x11.pdf

Secondary variable(s):

Immunogenicity Assessments

• Insulin Antibody test: Anti-insulin antibody (AIA)

Pharmacovigilance-Relevant Information

Not Applicable.

Data Quality Assurance

Audits and Inspections

Not applicable.

Data Handling

The Investigator maintained all documentation relating to this study. Essential documents (as defined in the ICH-GCP) are retained until at least 2-years after the last approval of a marketing application in an ICH region, and until there were no pending or contemplated marketing applications in an ICH region or at least 2-years have elapsed since the formal discontinuation of clinical development of the IP. These documents must be retained for a longer period, however, if required by the applicable regulatory requirement(s) or if needed by sponsor.

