Summary tables were provided for prior/concomitant medications in the study.

Immunogenicity analyses

Partial correlation was used to measure the relationship between the percent change in HbA1c and percent change in anti-insulin antibodies with absolute change in total insulin dose as covariate from baseline to Visit 7 and Visit 8. Change in level of serum anti-insulin antibodies from baseline to Visit 7 and Visit 8 were compared through paired t-test within each treatment arms.

Statistical Significance

The level of significance in the primary analysis were set to 5%. The analyses was performed upon completion of the main trial period. All secondary analyses were also be performed at the 5% significance level.

Replacement of Subjects

The subject who discontinued from trial/withdrawn from the study treatment were not replaced.

Withdrawn Subject Data Collection

The subject could withdraw their consent from the trial, or this could be the Investigator's decision to discontinue the subject from trial; if they decided to do so, at any time and irrespective of the reason all efforts should be made to document the reason for treatment withdrawal/discontinuation from the trial (see section 11.5.1) and this should be documented in the e-CRF.

The Investigator/designee involved in the study documented the reason for the subject withdrawal as follows:

Subject's voluntary withdrawal of consent

Subject's non-compliance to the IP: Repeated missing of study medication doses

Protocol violation: Repeated non-follow-up for safety or efficacy procedures required for the study. Protocol violation may be also considered when the subject is not included as per protocol-defined eligibility criteria.

Any AE or SAE requiring subject withdrawal in the opinion of the Investigator: An AE form must be completed. Clinically significant abnormal value not explained by a laboratory error or being not a known or abnormal value commonly observed in this type of population was also considered as an AE or SAE, and recorded on AE form as applicable.

Requirement of prohibited medication: Recording of the details of prohibited medication were completed on the concomitant medication CRF page and the subject were withdrawn from the study.

Requirement of dose reduction for both IP and non-IP: If there was requirement for change in dose of the IP (which is not mentioned in the protocol) or non-IP at any point of time during the study period, the subject were withdrawn from the study.

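### Incidence of treatment-emergent antibody response is named as the immunogenicity measure, but the supplied text neither defines it nor plans an analysis that estimates it

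*Combined protocol and SAP*

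**What the plan says.** The Secondary Objective is a single line: "To assess the immunogenicity of the investigational product". The section Discussion of Study Design, Including Choice of Control Group, then says how this is measured: "The immunogenicity was assessed by evaluating incidence of treatment-emergent antibody response (TEAR". TEAR is mentioned nowhere else, and no seroconversion rule, titre rise or assay cut-off is attached to it.

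The Immunogenicity Assessment section has blood taken at Visits 1, 7 and 8 "for testing presence of anti-insulin antibodies to the IP", using validated assays. The list of secondary variables names only the test: "Insulin Antibody test: Anti-insulin antibody (AIA".

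The Immunogenicity analyses section plans two things. The first is a correlation: "Partial correlation was used to measure the relationship between the percent change in HbA1c and percent change in anti-insulin antibodies", adjusted for change in insulin dose. The second is a test on level: "Change in level of serum anti-insulin antibodies from baseline to Visit 7 and Visit 8 were compared through paired t-test within each treatment arms". Under Statistical Significance, "All secondary analyses were also be performed at the 5% significance level".

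The statistical section describes itself as an outline and refers to a separate, more detailed SAP. Change in Planned Analysis is marked not applicable.

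**The concern.** The named measure is the share of subjects who develop an antibody response. Neither planned analysis estimates a share. The paired t-test asks whether the mean level in an arm moved. The correlation asks whether antibody change tracks HbA1c change, and percent change is undefined for any subject whose baseline antibody value is zero. The data categories listed under Safety Analysis do not name antibodies, so that section does not promise a responder count either.

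Two things are at stake. Followed as written, the supplied text yields no figure for the quantity it names. An arm with a few clear responders could also be reported as showing no significant antibody change, which a reader could take as evidence of low immunogenicity.

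**Working it through.** **Plan's own figure.** The documents give no antibody rate, SD or sample size for immunogenicity. The planned 52 per group is for the HbA1c paired t-test. The normal formula gives ((2.241 + 1.282)/0.5)² = 49.6, so 50. The exact t calculation gives 53, with 89.9% power at 52. The figure is close enough, but it does not bear on this point.

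**Inputs.**
- Arm size, from Overview of Study Design: "Total of 153 subjects who met the eligibility criteria were randomized in a ratio of 1:1:1", so 153/3 = 51.
- Significance level, from Statistical Significance: 5%. Two-sided is assumed, because the section does not say.
- Critical t on 50 degrees of freedom: 2.009.

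**Step 1: limit for a few responders, whatever the size of their rise.** Let k of n subjects rise by the same amount D and the rest not change.
- Mean change = kD/n.
- Variance of change = D²·k(n−k)/[n(n−1)].
- t = mean/(SD/√n) = √[k(n−1)/(n−k)].

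D cancels, because each responder raises the SD along with the mean. Equal rises are the most favourable case for the test, since unequal rises with the same total only increase the SD. With n = 51:

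| Responders k | t = √[50k/(51−k)] | Two-sided p |
|---|---|---|
| 1 | √(50/50) = 1.00 | 0.32 |
| 2 | √(100/49) = 1.43 | 0.16 |
| 3 | √(150/48) = 1.77 | 0.083 |
| 4 | √(200/47) = 2.06 | 0.044 |

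Up to three responders cannot reach 5% in this setting, and four can. If 20% of the arm were lost (51 × 0.8 ≈ 41 remaining), three responders give √(120/38) = 1.78 against a critical value of 2.021, so the conclusion is the same.

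**Step 2: adding noise in the non-responders.** With an SD of change of 1 (assumed), three responders give rejection in 17% of simulated trials at a rise of 5 SD, 18% at 10 SD, 10% at 20 SD and 0.2% at 50 SD. The rate ends up falling as the response grows, as step 1 predicts. With five responders it is 46%, 73%, 96% and essentially 100% at the same rises.

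**Step 3: one scenario across a range of responder counts.** Assumed: non-responders change by 0 on average, SD 1; responders rise by 9, SD 3; n = 51; 40,000 simulated arms per row. The last column is the incidence with its Clopper-Pearson interval for the same count.

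| Responders | t-test rejects | Incidence (exact 95% CI) |
|---|---|---|
| 3 | about 15% | 5.9% (1.2 to 16.2) |
| 4 | about 34% | 7.8% (2.2 to 18.9) |
| 5 | about 61% | 9.8% (3.3 to 21.4) |
| 6 | about 84% | 11.8% (4.4 to 23.9) |
| 8 | about 99% | 15.7% (7.0 to 28.6) |

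The two result columns are different quantities, a rejection rate and an estimate. They are placed together only to show what each method would report. With no responders, 0/51 still gives an informative upper limit of 7.0%.

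**The case against.** The strongest reply is that the supplied text is an outline. A separate SAP is said to hold the detail, and it may define TEAR and tabulate it. The sentence naming TEAR is never withdrawn. A reader might infer that the sponsor replaced the endpoint, or that the trial will report no incidence. The documents support neither. They show only that the supplied analysis section is silent on the named measure. That caveat stands, but it does not fill the gap in the text available for review.

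Second, a reader might say that the objective is about a few strong responders. Its wording is general, and change in level is a legitimate aspect of immunogenicity. The interest in responders comes from the choice of an incidence in the design discussion.

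Third, the scenario rests on invented inputs, and no distribution of antibody values is given. If responses are common, the t-test finds them: 84% at six responders and 99% at eight. This is why the result is shown over a range. Step 1 needs no assumed size of rise, but it does assume that the other subjects do not change.

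Fourth, a reader might treat the lack of a comparison of antibody responders between doses as a departure from the plan. The plan promises an incidence and not a comparison of incidences. Such a comparison would also be weak: a two-sided exact trend test gives p = 0.14 for 1, 3 and 5 responders of 51, and 0.58 for 3, 4 and 5.

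**Conclusion.** The concern holds in this form: on the supplied text, the measure named for the only secondary objective is undefined and has no analysis that estimates it. The planned mean-level test is not a substitute. With 51 per arm, no change in the other subjects and 5% two-sided, it cannot reach significance with up to three equal responders (5.9%), whatever their rise. In the assumed scenario the loss is large at three to five responders and small by eight, so it should not be read as a general failure of the t-test. The mismatch between endpoint and analysis does not depend on any of these assumptions. The separate SAP, if it defines and tabulates TEAR, could close the point. The HbA1c analysis is unaffected.

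**What to change.** In Immunogenicity analyses, make TEAR incidence the analysis of the secondary objective.

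- **Definition.** Count a subject who is antibody-negative at screening and positive later, or positive at screening with a rise beyond a limit taken from the validated assay. Fix that limit without reference to the trial's results.
- **Reporting.** Give number, percent and exact 95% CI per arm at Visits 7 and 8, with the denominator stated.
- **Existing analyses.** Keep the antibody-level analysis as supportive. A trend test across doses is optional and has little power.
- **Labelling.** The document is written in the past tense. If the definition is added after data collection and is not in the separate SAP, identify the analysis as post hoc in the clinical study report, as the section on deviations from the statistical plan requires. If the separate SAP already contains the definition and table, a cross-reference is enough.

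The cost is one extra table and a few lines of text, from samples already scheduled at Visits 1, 7 and 8. The drawback is a possible post hoc label on the main immunogenicity result.
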